#### 2.5 CASE REPORT FORMS

Example Case Report Forms are provided in Appendix B. A forms notebook for each patient will be provided by the sponsor. The notebook is designed to make keeping the records for the study more organized and to reduce the potential for mixing up data. Extra forms will be provided on request, or as needed.

# 3.0 DEVICE DESCRIPTION AND RISK ANALYSIS (17mm aortic and 23mm mitral)

The On-XTM prosthesis is a bileaflet mechanical heart valve prosthesis. The housing consists of On-X® pyrolytic carbon coating on a graphite substrate. In other sizes the On-X valve has been in clinical use since 1996 and has been approved for commercial distribution in the US since 2001 (aortic valves) and 2002 (mitral valves).

Two radiopaque leaflets are constrained by pivots in the housing walls. The leaflets are  $On-X^{\otimes}$  pyrolytic carbon deposited on a graphite substrate which is mixed with 10 weight % tungsten to allow for radiographic visualization. In the closed position, the occluders rest at 40° within the valve orifice. The valve design permits maximum leaflet opening angles of 90° from the plane of the housing, a position that follows flow. The pivot design includes features that enhance and ensure closure response to reverse flow and opening response to forward flow.

The rotatable sewing ring is made from polytetrafluoroethylene (PTFE) fabric attached to the valve housing by means of titanium retaining rings and 5-0 suture material. The retaining rings positively attach the sewing ring to the valve housing by straddling a flange on the housing OD. They also provide the means for radiographic visualization and identification. There are no coatings or treatments on the fabric, although black orientation marks are included on the ring fabric. The sewing rings are supra-annular and allow the tissue annulus to abut the pyrolytic carbon housing

directly, except in sizes larger than 25 mm, where the sewing rings become intraannular to allow the 25 mm housing (largest size made) to fit properly into larger tissue annuli.

Valves are packaged on a valve holder /rotator with a separately packaged, removable handle to facilitate insertion and in situ orientation, and to provide protection during shipment and handling. The package is designed for shipment protection as well as handling ease. Valves are surgically clean and have been sterilized. The instructions for use packaged with the valve describe the handling of the valve during surgery in detail. Adhere to all instructions, warnings and precautions in the labeling. Reusable valve sizers, rotators, handles and leaflet motion probes are provided non-sterile in a separate accessory kit. These devices are designed to aid the proper selection and implantation of the On-X® valve, and should be cleaned and sterilized in accordance with their instructions prior to each use.

The subjects for whom this device is intended are those seriously or critically ill patients whose prognosis without surgery for replacement or repair of the diseased natural or prosthetic valve is unacceptably poor in terms of survival, quality of life, or both in the opinion of the attending physicians, based upon the patient's disease history and physical and laboratory findings from standard cardiovascular diagnostic workups and who require a smaller than currently available valve size. For this special subset of patients there are a number of widely accepted prosthetic heart valves in common use. All prosthetic heart valve implants carry risks of serious complications, and/or death, related to thrombogenicity, hemodynamics and durability, among other causes. Valvular reconstruction is also an option for this patient population, but not for all cases or conditions.

The purpose of this investigation is to establish the hemodynamics, hemolytic potential and valve-related complication rates of a smaller On-X® prosthetic heart valve. The use of the valve is not expected, based on existing clinical and preclinical study results, to carry any increased risk over those of other mechanical heart valves. All diagnostic procedures included in the investigation are standard to the postoperative care of heart valve patients. The normal diagnostic procedures used include blood tests from standard venipuncture draws, and physical examination, which are either non-invasive or minimally invasive with little or no risk to the patient. Hazardous invasive techniques, such as cardiac catheterization, are not generally used, and are not expected to occur. Reoperations will be conducted only when a complication creates a need for such action, and these events cause the same intervention for presently available prostheses.

The use of modern cardiopulmonary bypass techniques; including cold cardioplegia, are expected to minimize operative risk consistent with the standards of practice for open heart surgery. The use of properly balanced anticoagulant therapy along with explicit instructions to patients regarding the importance of their drug therapy, are expected to bring about an optimal balance between thrombotic and hemorrhagic

complications. Additional instructions to patients and their referring physicians are useful in minimizing complications, such as prosthetic endocarditis.

Because the On-X® valve in a small size has demonstrated performance meeting or exceeding standards requirements in preclinical studies and in its clinical history in larger sizes has established reasonable safety and effectiveness, it is reasonable to continue to investigate this device to expand the size range available for human subjects under the controlled conditions described in the protocol, and within the patient population also described.

#### 4.0 LABELING

A copy of the device label is contained in Appendix E. The labeling consists of the standard box label for the On-X valve used in production units with the investigational device label added. The IFU in the box is also the standard production IFU with an insert sheet for the 17mm aortic valve and the investigational label added. This size valve has been used internationally for over 15 years, but is not available in the US due to lack of hemodynamic or blood damage data.

# APPENDIX A

# COMPLETE ECHOCARDIOGRAPHY PROTOCOL

#### ON-X LIFE TECHNOLOGIES

#### On-X® 17mm AORTIC/23mm MITRAL STUDY

#### **ECHOCARDIOGRAPHIC PROCEDURES**

- 1. General interobserver and intraobserver variability
- 1.1 At each center, no more than two operators should perform studies.
- 1.2 At each center, one or at most two machines will be used for the study. Velocity data will be calibrated using a string phantom or equivalent device.

#### 2. Exclusions

2.1 Poor echocardiographic window

#### 3. Recording studies

- 3.1 Unless impossible, every study will include the following standard imaging views: parasternal long-axis, parasternal short-axis, apical 4-chamber, apical 2-chamber, apical long-axis and subcostal. Off-axis views as appropriate will also be necessary particularly to look for paraprosthetic regurgitation.
- 3.2 Doppler recordings will be made with a stand-alone continuous wave probe from apical views and for valves in the aortic position from additional right intercostals or suprasternal views. Both orthograde waveforms and, if present, regurgitant jets will be recorded.
- 3.3 Subaortic pulsed recordings will be made in the apical 5-chamber view with the sample placed just below the level at which significant flow acceleration occurs.
- 3.4 Recordings should be made with the scale set to maximize signal size and with the maximum available sweep speed.
- 3.5 All images and waveforms used for calculating information will be recorded on electronic media.

#### 4. Data collected

Heart rate (BPM), height (cm) and weight (kg) are collected by the most convenient measure at the time of the echo exam. Body surface area (BSA) is determined from the standard nomogram or standard equation below. Geometric orifice area (GOA) is given by valve size in Table 8 of the On-X valve instructions for use. BSA ( $m^2$ ) = (Wt(kg)0.425 X Ht(cm)0.725) X 0.007184.

- 4.2 Diameter of the left ventricular outflow tract measured on three parasternal long-axis frames frozen in systole. Diameters will be measured from the trailing edge of the left septal echo to the leading edge of the anterior mitral leaflet echo. The maximum dimension will be taken. If there is reverberation artifact from calcium, the leading edge to leading edge convention will be used; if this artifact is excessive, the measurement will not be made. The best measurement (usually at the preoperative examination) will be assumed to remain constant throughout the study. If measurement is not practical for pediatric patients the aortic tissue annulus diameter of the valve will be used, and the measurement will not be made for the mitral valve.
- 4.3 From the subaortic waveform (for prostheses in mitral or aortic positions): **peak** velocity  $(v_1)$ , mean pressure  $(\Delta P_1)$  calculated by echo machine software, velocity integral  $(VTI_1)$ .
- 4.4 From the transacrtic waveform (prostheses in the acrtic position only): peak velocity  $(v_2)$ , mean pressure  $(\Delta P_2)$  calculated by echo machine software, velocity integral  $(VTI_2)$ .
- From the mitral waveform (prostheses in the mitral position only): Pressure half-time (PHT), mean pressure drop ( $\Delta P_m$ ), peak instantaneous early velocity ( $v_m$ ), diastolic velocity integral (DVI).
- 4.6 Doppler measurements will be made over 3 cycles in sinus rhythm or over 5 to 10 cycles in atrial fibrillation (depending on clinical judgment). These will then be averaged.
- 5. Calculations

The data collected will be entered on a database and the following calculations will be performed at the central laboratory:

5.1 Effective area by the continuity equation (EOA) in the aortic position:  $EOA = CSA \times VTI_1 / VTI_2$  [1]

where CSA is left ventricular outflow cross-sectional area in cm^2 calculated from the diameter assuming circular cross-section; VTI1 is subaortic velocity integral in cm and VTI2 is aortic velocity integral in cm.

5.2 Effective area by the continuity equation (MOA) in the mitral position: MOA = CSA x VTI1 / DVI [2]

where DVI is diastolic velocity integral in cm

5.3 Effective area by the pressure half-time method (MOA1/2) in the mitral position:

MOA1/2 = 220/PHT

[3]

5.4 Peak pressure drop across the aortic valve:

Peak  $\Delta P = 4 (v_2^2 - v_1^2)$ 

[4]

5.5 Mean pressure difference across the aortic valve (per ISO requirement):

Mean  $\Delta P = \Delta P_2 - \Delta P_1$  [5] (Per ISO 5840 – mean  $\Delta P$  = aortic  $\Delta P$  – subaortic  $\Delta P$ )

5.6 Peak pressure drop across the mitral valve:

Peak  $\Delta P = 4v_m^2$ 

[6]

5.7 Cardiac Output:

 $CO = CSA \times VTI_1 \times BPM$  [7]

5.8 Indexed effective orifice areas (EOAI), and cardiac index (CI):

EOAI = EOA/BSA [8]; CI = CO/BSA [9]

5.9 Performance Index (PI):

PI = EOA/GOA [10]

6. Other analyses

- 6.1 For valves in the aortic position, mean and standard deviation values will be calculated for the following parameters: peak transaortic velocity, mean transaortic velocity, mean pressure difference, peak pressure difference, effective orifice area, cardiac output and all indices.
- 6.2 For valves in the mitral position, mean and standard deviation values will be calculated for the following parameters: peak transmitral velocity, peak transmitral pressure difference, mean transmitral pressure difference, effective orifice area by continuity equation, pressure half-time and effective orifice area by pressure half-time, cardiac output and all indices.
- 6.3 The site and severity of a rtic regurgitation and mitral regurgitation will be assessed.
- 6.4 The presence, site and size of any thrombus will be assessed.

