#### 1.0 PURPOSE

The purpose of the proposed study is to assess the safety and efficacy of the 17mm On-X Aortic Prosthetic Heart Valve when used to replace diseased aortic valves and the 23mm On-X Mitral Prosthetic Heart Valve when used to replace diseased mitral valves in human subjects.

The On-X 17mm aortic valve will be implanted in approximately 20 and at least 15 patients and will be followed for 1 year. Enrollment of On-X 23mm mitral valve patients has been discontinued due to low enrollment potential. Follow-up of enrolled patients will continue according to the protocol for 1 year.

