#### 2.1 STUDY DESIGN (SAMPLE SIZE)

Patients meeting all the appropriate criteria will be recruited for clinical trial participation. Enrollment is non-randomized, and continues until the sample size requirement is met, unless the sponsor terminates the clinical trial early for unforeseen reasons.

Submission for premarket approval in the U.S. will occur after international standards criterion of at least 15 patients will be followed for one year. This follow-up will include echocardiography, blood damage, NYHA status and any adverse events.

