#### 2.2 PATIENT POPULATION AND SELECTION CRITERIA

The indications for replacement of a patient's natural or prosthetic valve will be those which the principal investigator follows in his routine practice of cardiovascular surgery.

The following are criteria for inclusion of patients in this study:

- 1. Patients of any age; unless waived by local IRB assent of the patient and in all cases consent of parent or legally authorized representative is required if a patient is under the age of majority and not legally emancipated.
- 2. Patients who are sufficiently ill to warrant replacement of their diseased natural or prosthetic valve, based on standard cardiovascular diagnostic workups.
- 3. Patients who are in sufficient satisfactory condition, based on the physical exam and investigator's experience, to be an average or better operative risk, (i.e., likely to survive one year postoperatively).
- 4. Patients who require an isolated aortic valve replacement size 17 mm.
- 5. Patients who are geographically stable and willing to return to the implanting center for follow-up visits.

- 6. Patients or legally authorized representatives who are adequately informed of their participation in the clinical study and what will be required of them in order to comply with the protocol.
- 7. Patients requiring concomitant cardiovascular surgery, such as coronary bypass may be included in the study.

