#### 2.3 INSTITUTIONAL REVIEW AND INFORMED CONSENT

Institutional review through the appropriate standing committee of the clinical center (either Ethics Committee or Institutional Review Board) must be obtained as required by local rules, and a copy of the approval document must be supplied to the sponsor. A list is contained in Appendix F.

Informed consent must be obtained for each patient prior to participation in the clinical trial in accordance with local rules. As this study includes some pediatric patients, consent shall include assent of the patient as well as consent of his/her parent or legally authorized representative whenever such patient is recruited. Assent may be waived by the local IRB if the patient is incapable due to age, maturity or psychological state. Local IRB rules or individual case review can be used to determine if waiver is appropriate, which if not addressed in the IRB approval document must be obtained case-by-case. It is the responsibility of the principal investigator to obtain such waiver prospectively as needed. A copy of the informed consent should be provided to the patient or representative and they should be encouraged to review it. It is recommended that the informed consent be reviewed as part of the preoperative procedures with prospective enrollment. An example informed consent document is in Appendix C.

Each clinical center must have a staff echocardiologist responsible for conduction of the echocardiographic portions of this study. Additionally, coagulation profiles are to be reported as the international normalized ratio (INR), and hemolysis study blood samples must be sent to a local laboratory and the laboratory normal ranges must be supplied to the sponsor.

This study also requires that copies of all echocardiography electronic recordings be sent to the sponsor for review.

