#### 2.4.1. Preoperative Procedures

The investigator will determine and document on CRFs whether each patient meets the selection criteria previously outlined before enrollment into the study. He will also obtain informed consent for study participation from each patient prior to enrollment. A copy of the informed consent form will be kept by the investigator in the patient's study notebook. Patients not meeting the selection criteria or not receiving informed consent **should not** be enrolled in the study.

The investigator will determine and record on CRF1 each patient's demographics and relevant medical history, i.e., New York Heart Association (NYHA) functional class, cardiac rhythm, preoperative conditions, and diagnosis for valve replacement, etc. A preoperative echo/Doppler evaluation of the valve(s) being replaced is required according to the procedures of this study; a cardiac catheterization is not requested.

Blood studies on each patient will include: white blood cell count, red blood cell count, hemoglobin, hematocrit, serum lactate dehydrogenase (with fractionation by isoenzymes if above normal), plasma free hemoglobin, reticulocyte count, and haptoglobin. This will be recorded preoperatively, if possible, and at both follow-up intervals. The laboratory report including normal ranges will suffice as a CRF for these tests.

Specific Instructions for Form CRF1

These instructions are made to assist the study coordinator in filling out the form. Complete all items on the form. If information is unavailable to answer any item, make a note on the form. When asked to specify a particular answer, use a short description. On all check off lists, the space to be checked is either in front of, or below the answer. Please check any and all items that apply to the patient.

For patient study ID use patient initials. NYHA functional class uses the generally familiar nomenclature of that association. For the purposes of this study the commonly used classes of IIa and IIb are not used, either subgroup is considered class II. For infants and toddlers the Ross Scale functional classification can be substituted for NYHA classification anytime this data element is requested.

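### Any age is eligible, but aortic hemodynamics are summarised as one mean and SD with no breakdown by age or body size, so a few small children can raise and widen the pooled indexed EOA

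*Combined protocol and SAP*

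**What the plan says.** **Who can enter.** Inclusion 1 in section 2.2 sets no age limit: "Patients of any age; unless waived by local IRB assent of the patient" is followed by the consent rule for minors. Section 2.3 treats children as part of the trial: "As this study includes some pediatric patients, consent shall include assent of the patient". Section 2.4.1 foresees very young ones: "For infants and toddlers the Ross Scale functional classification can be substituted for NYHA classification". Section 2.2.1 directs screening to small patients. It does not expect BSA above 1.8 m2, it screens those below 1.5 m2, and it sets no lower bound.

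**How many.** Section 1.0: "The On-X 17mm aortic valve will be implanted in approximately 20 and at least 15 patients". Section 2.1 ties the minimum to an "international standards criterion of at least 15 patients will be followed for one year".

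**How hemodynamics are summarised.** Appendix A 6.1: "For valves in the aortic position, mean and standard deviation values will be calculated for the following parameters". The list that follows covers velocities, pressure differences, EOA, cardiac output and all the indices. Section 2.0 (Valve effectiveness) calls for standard descriptive statistics and a comparison with the PMA data by valve position. Section 2.4.10 adds a t-test or chi-square test against the PMA results at matching times. Valve position is the only split named in these places.

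**Where children are handled differently.** They have a substitute for NYHA class, a comorbidity entry on CRF1, and a substitute for the outflow diameter. If that diameter cannot be measured in a child, the nominal 17 mm is used (section 2.4.6; Appendix A 4.2). None of these differences is carried into the analysis.

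**The concern.** Every study valve in the aortic group is the same size, but the patients may range from toddlers to adults. EOAI divides a quantity set largely by the valve by one set by the patient. A pooled mean therefore depends on how many small patients happen to enrol, and with two clusters it may describe neither.

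This matters because section 4.0 says the 17 mm size is not available in the US for want of hemodynamic or blood damage data, so these summaries are a main product of the trial. A reader given only the pooled mean and SD could not recover the adult value. The same pooled figures also feed the t-test in section 2.4.10.

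The diameter substitution adds a second mixture. EOA, EOAI, cardiac output, cardiac index and performance index all use the outflow area, so for these measures the pooled summary can combine two measurement methods. The pressure formulas [4] and [5] do not use it.

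**Working it through.** **No figure to reproduce.** The documents give no expected EOAI, gradient, SD, effect size or number of children. The minimum of 15 comes from a standard, not from a power calculation. What follows is an illustration.

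**From the documents:** N = 15 or 20 (section 1.0) and EOAI = EOA/BSA (Appendix A [8]).

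**Assumed:** EOA 1.2 cm2 in every patient; adult BSA 1.5 m2 (the lower screening figure in section 2.2.1); child BSA 0.7 m2, range 0.5 to 1.0; k = 1, 3 or 5 children; within-group coefficient of variation 15%.

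**Mean EOAI.**
- Adult: 1.2/1.5 = 0.80 cm2/m2. Child: 1.2/0.7 = 1.71.
- N = 15, k = 3: (12 × 0.80 + 3 × 1.714)/15 = 0.983, or +23%.
- N = 20, k = 3: (17 × 0.80 + 3 × 1.714)/20 = 0.937, or +17%.

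The relative shift is (k/N) × (adult BSA/child BSA − 1), so the assumed EOA cancels:

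| Child BSA (m2) | k=1, N=15 | k=3, N=15 | k=5, N=15 | k=3, N=20 |
|---|---|---|---|---|
| 0.5 | +13% | +40% | +67% | +30% |
| 0.7 | +8% | +23% | +38% | +17% |
| 1.0 | +3% | +10% | +17% | +7.5% |

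With k = 0 the shift is zero.

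**SD of EOAI, 3 of 15.** The within-group SDs are 0.15 × 0.80 = 0.12 and 0.15 × 1.714 = 0.257.
- Within-group variance: 0.8 × 0.12² + 0.2 × 0.257² = 0.025.
- Between-group variance: 0.2 × 0.8 × (1.714 − 0.80)² = 0.134.
- Pooled SD: √0.159 ≈ 0.40, against 0.12 in adults alone.

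**Second set of assumptions.** With EOA 1.1 cm2, child BSA 0.8 and a within-group SD of 0.15, 3 of 15 children move the mean from 0.73 to 0.86 (+17.5%) and the SD from 0.15 to about 0.31.

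**When the direction reverses.** Pooled EOAI falls only if child EOA is below (child BSA/adult BSA) × adult EOA. That is 0.7/1.5 = 0.47 of the adult value at BSA 0.7, and 0.8/1.5 = 0.53 at BSA 0.8.

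**Mean gradient.** No formula in the documents gives a direction, so I assumed that at equal EOA the gradient scales with flow squared.
- Simple model: child/adult ratio = (child BSA × c/1.5)², where c is the child/adult ratio of cardiac index. With 3 of 15 children and BSA 0.7, the pooled change is 0.2 × (0.467² − 1) = −15.6% at c = 1, and 0.2 × (0.70² − 1) = −10.2% at c = 1.5. At BSA 1.0 and c = 1.5 the ratio is 1 and nothing changes.
- Fuller model: flow = cardiac index × BSA/(heart rate × ejection time). Assumed for adults: BSA 1.5, index 2.8, rate 75, ejection time 0.30 s. Assumed for children: index 3 to 5, with rate 90 and 0.27 s or rate 110 and 0.24 s. With 3 of 15 children the pooled change is −17% to −4% at child BSA 0.6 to 0.8, −13% to +4% at 1.0, and −9% to +15% at 1.2.

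The gradient can therefore move either way.

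**The case against.** **Pooling is inferred from silence.** 6.1 lists parameters; it neither mentions children nor forbids a breakdown. That is fair, but no other section supplies one, so the plan as written yields a single mean and SD.

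**A pooled mean correctly describes those enrolled, and a high EOAI in a small patient is a true value.** This stands. The problem is what the summary hides, not that any value is biased.

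**The size rests on assumptions.** This stands too. The number of children is unknown. The need for a 17 mm valve (inclusion 4) limits how small a child can be, so the 0.5 m2 row is an extreme. Equal EOA is assumed, and the nominal-diameter rule adds error of unknown direction. EOA itself and performance index (EOA/GOA) are not divided by BSA and are not shifted by this mechanism.

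**The protocol already warns about small numbers.** Section 2.4.10 concedes limited power and promises to assess it. That does not address a mixture of body sizes.

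**A stronger reading is tempting.** A reader might infer that children raise EOAI and lower the gradient, and so flatter the device. The documents do not support this. The sign of the gradient shift can reverse at a child BSA of about 1.0 m2 or more. No success threshold is stated for either measure. The age and BSA mix of the PMA data is not given, and a wider SD makes a difference from the PMA data harder to detect.

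**Splitting at the age of majority would be a poor main remedy.** BSA drives the effect, the legal age may differ between US and non-US sites, and one to three children cannot support a mean and SD. I agree, and the fix does not rest on that split.

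**Conclusion.** The point holds as a reporting gap. Children are an expected part of a group of 15 to 20, and the planned summary has no breakdown by age or body size. At equal EOA, small children raise pooled mean EOAI and inflate its SD. Under the stated assumptions, three children of BSA 0.7 m2 give +23% at N = 15 and +17% at N = 20, with the SD rising from 0.12 to about 0.40 at N = 15. The upward direction for EOAI follows from the protocol's own formula unless child EOA falls to about half the adult value or less. The size is illustrative, and it is zero without children.

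For gradients, the most that can be said is that pooling may shift the mean in a direction that depends on flow. Nothing shows that pooling favours the device in the PMA comparison.

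**What to change.** Amend Appendix A 6.1, and carry the change into section 2.4.10, so that at each visit:

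- EOAI and mean gradient are listed per patient with age and BSA, and plotted against BSA.
- Mean and SD are also given for adults alone, and pediatric patients are listed individually rather than averaged.
- Patients whose outflow diameter was replaced by the nominal 17 mm are flagged.
- The pooled figures stay alongside.

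No formal subgroup test is needed, and 15 to 20 patients could not support one.

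The cost is analysis wording only. Date of birth is on CRF1, BSA is on CRF2, and the core laboratory that derives the areas can record when it used the nominal diameter. The small downside is that the adult-only mean rests on fewer patients.
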